11.2. Adverse Events of Special Interest

The following TEAEs of special interest (AESI) will be summarized by SOC and PT:

- Diarrhea / Colitis
- Pneumonitis / Interstitial lung disease (ILD)
- Hepatitis and increases in transaminases
- Endocrinopathies (adrenal insufficiency, hyperthyroidism, hypothyroidism, hypophysitis / hypopituitarism, and Type I diabetes mellitus)
- Dermatitis / rash and pruritis
- Nephritis and increases in serum creatinine
- Neuromuscular toxicity (e.g. Guillain-Barré and myasthenia gravis)
- Pancreatitis (or labs suggestive of pancreatitis – increased serum lipase or increased serum amylase)
- Infusion Reactions
- Hypersensitivity Reactions

11.3. Clinical Laboratory Evaluations

Clinical laboratory values from the central laboratories (hematology and chemistry) will be graded according to NCI CTCAE Version 4.03 or higher for applicable tests. The worst grade during the treatment period will be summarized. Frequency distributions for shift from baseline to the worst grade during the treatment period will be presented.

Clinical laboratory values from the central laboratories will also be summarized descriptively (N, mean, StdDev, median, Min, and Max).

Listings of clinical laboratory data from the central laboratory and also from the local laboratory (hematology, chemistry, coagulation, thyroid function tests, renal function assessment) with abnormal flags will be provided by subjects and tests.

11.4. Vital Sign Measurements

For vital signs, the shift from baseline to worst during the treatment in below, within, and above the normal ranges will be displayed in cross-tabulations for each treatment. Summary statistics (N, mean, StdDev, median, Min, and Max) of observed values and change from baseline values will be presented.

11.5. Electrocardiograms

The overall ECG interpretation will be summarized by presenting the number and percentage of subjects with 'Normal', 'Abnormal, not clinically significant', and 'Abnormal, clinically significant' by treatment arm. The shift from baseline to worst during treatment in the overall ECG interpretation will be displayed in cross-tabulations.

11.6. Eastern Cooperative Oncology Group Performance Status

A shift table from baseline to best post baseline ECOG PS score will be displayed in cross-tabulations. A listing of ECOG PS scores will also be provided.

11.7. Other Assessments

Categorical characteristics like non-measurable plasmacytoma assessment will be summarized using frequency counts and percentages for the Full Analysis Set Population, by visit.

Continuous variables like measurable plasmacytoma assessment will be summarized by descriptive statistics for observed values and the change from baseline (mean, StdDev, median, Min, and Max).

11.8. Pharmacokinetic Analysis

Pharmacokinetic analysis will be based on the PK population. Non-compartmental PK parameters such as time to maximum concentration (T_{max}), maximum observed concentration (C_{max}), area under the curve (AUC), terminal elimination half-life (t_{1/2}), clearance (CL/F), and volume of distribution (V_z/F) will be estimated from the plasma concentration-time profile for DURVA. For DARA, typical serum PK parameters, such as C_{max}, AUC, T_{max}, t_{1/2}, CL/F and V_z/F will be summarized. All concentration data and PK parameters will be summarized descriptively.

13. INTERIM ANALYSIS

This study will be conducted in 2 parts with two interim analyses being planned.

The first interim analysis will be conducted at the end of Stage 1 of Part 1, when the first 18 subjects enrolled have completed at least 3 cycles of treatment. If at least 3 subjects out of 18 achieve a response (PR or better), the study will continue to Stage 2. The second interim analysis will be conducted at the end of Stage 2. If at least 9 subjects achieve a response (PR or better) out of a total of 50 subjects and it is determined by the Sponsor to further confirm the efficacy and safety of D², an additional 70 subjects may be enrolled.

CELGENE PROPRIETARY INFORMATION

**14. CHANGES TO THE STATISTICAL ANALYSES SECTION OF
THE PROTOCOL**

Not applicable.

CELGENE PROPRIETARY INFORMATION

16. APPENDICES

16.1. Handling of Dates

Dates will be stored as numeric variables in the SAS analysis files and reported in DDMMYY format (ie, the Date9. datetime format in SAS). Dates in the clinical database are classified into the categories of procedure dates, log dates, milestone dates, outcome dates, and special dates.

- **Procedure Dates** are the dates on which given protocol-specified procedure are performed. They include the dates of laboratory testing, physical examinations, tumor scans, etc. They should be present whenever data for a protocol-specified procedure are present and should only be missing when a procedure are marked as NOT DONE in the database. Procedure dates will not be imputed.
- **Log Dates** are dates recorded in CRF data logs. Specifically, they are the start and end dates for adverse events and concomitant medications/procedures. They should not be missing unless an event or medication is marked as *ongoing* in the database. Otherwise, incomplete log dates will be imputed according to the rules in Appendix 16.2 (eg, for duration or cycle assignment, etc). However, in listings, log dates will be shown as recorded without imputation.
- **Milestone Dates** are dates of protocol milestones such as randomization, study drug start date, study drug termination date, study closure date, etc. They should not be missing if the milestone occurs for a subject. They will not be imputed.
- **Outcome Dates** are dates corresponding to study endpoints such as survival, progression, etc. In most cases they are derived either from a milestone (eg, the survival date is derived from the death date), or a procedure date (eg, the progression date is derived from the date of the tumor scan that was used to determine progression). They may be subject to endpoint-specific censoring rules if the outcome did not occur, but are not otherwise subject to imputation.
- **Special Dates** cannot be classified in any of the above categories and they include the date of birth. They may be subject to variable-specific censoring and imputation rules.

Dates recorded in comment fields will not be imputed or reported in any specific format.

16.1.1. Calculation Using Dates

Calculations using dates (eg, subject's age or relative day after the first dose of study drug) will adhere to the following conventions:

- Study days after the start day of study drug will be calculated as the difference between the date of interest and the first date of dosing of study drug (eg, durvalumab) plus 1 day. The generalized calculation algorithm for relative day is the following:

- If TARGET DATE \geq DSTART then STUDY DAY = (TARGET DATE – DSTART) + 1;
- Else use STUDY DAY = TARGET DATE – DSTART.

Note that Study Day 1 is the first day of treatment of study drug. Negative study days are reflective of observations obtained during the baseline/screening period. Note: Partial dates for the first study drug are not imputed in general. All effort should be made to avoid incomplete study drug start dates.

- Age (expressed in days) is calculated: AGE = CONSENT – DATE of BIRTH + 1. In practice, age will be transformed to years by dividing the difference by 365.25 days, then truncating.
 - Preference is for using calculated age from clinical database. When not available, calculated age from CRF or interactive voice response system (IVRS) may be used. If only a partial birth date is given then the age as reported in the CRF will be used.
 - Intervals that are presented in weeks will be transformed from days to weeks by using (without truncation) the following conversion formula:

$$\text{WEEKS} = \text{DAYS} / 7$$

- Intervals that are presented in months will be transformed from days to months by using (without truncation) the following conversion formula:

$$\text{MONTHS} = \text{DAYS} / 30.4167$$

16.1.2. Calculation of Cycles

The start date of each treatment cycle will be calculated based on study drug exposure records for each subject. The start date of the first cycle will be the date when the subject receives any dose of study drug.

Once the start dates, eg, $S_1, S_2, S_3\dots$ are calculated, the end date of each cycle is calculated as the day before the start date of the following cycle, ie, $E_i = S_{i+1} - 1$. For the last cycle, the end date will be calculated as the start date plus prescribed cycle length, or the treatment discontinuation date, or the death date, whichever is earlier. If a date is on or after S_i and before S_{i+1} , the corresponding cycle number will be i .

16.2. Date Imputation Guideline

16.2.1. Impute Missing Adverse Events / Prior or Concomitant Medications

Incomplete Start Date:

Missing day and month

- If the year is the **same** as the year of the first dosing date, then the day and month of the first dosing date will be assigned to the missing fields.

- If the year is **prior to** the year of first dosing date, then December 31 will be assigned to the missing fields.
- If the year is **after** the year of first dosing, then January 1 will be assigned to the missing fields.

Missing day only

- If the month and year are the **same** as the year and month of first dosing date, then the first dosing date will be assigned to the missing day.
- If either the year of the partial date is **before** the year of the first dosing date or the years of the partial date and the first dosing date are the same but the month of partial date is **before** the month of the first dosing date, then the last day of the month will be assigned to the missing day.
- If either the year of the partial date is **after** the year of the first dosing date or the years of the partial date and the first dose date are the same but the month of partial date is **after** the month of the first dosing date, then the first day of the month will be assigned to the missing day.

Missing day, month, and year

No imputation is needed; the corresponding AE will be included as TEAE.

Incomplete Start Date: If the imputed start date is after the stop date, then the start date will be imputed by the stop date

Incomplete Stop Date: If the imputed stop date is before the start date, then the imputed stop date will be equal to the start date.

Missing day and month

- If the year of the incomplete stop date is the **same** as the year of the last dosing date, then the day and month of the last dosing date will be assigned to the missing fields.
- If the year of the incomplete stop date is **prior to** the year of the last dosing date or prior to the year of the first dosing date, then December 31 will be assigned to the missing fields.
- If the year of the incomplete stop date is **prior to** the year of the last dosing date but is the same as the year of the first dosing date, then the first dosing date will be assigned to the missing date.
- If the year of the incomplete stop date is **after** the year of the last dosing date, then January 1 will be assigned to the missing fields.

Missing day only

- If the month and year of the incomplete stop date are the **same** as the month and year of the last dosing date, then the day of the last dosing date will be assigned to the missing day.
- If either the year of the partial date is **not equal to** the year of the last dosing date or the years of the partial date and the last dosing date are the same but the month of partial date is **not equal to** the month of the last dosing date, then the last day of the month will be assigned to the missing day.

16.2.2. Adverse Events

Partially missing AE start dates will be imputed in the analysis data model (ADaM) dataset for AEs, but partially missing AE end dates will not be imputed in the same dataset. If the AE end date is complete with no missing year, month, or day, and the partially missing start date imputed by the rules below is after the AE end date, then the start date will be imputed by the AE end date.

16.2.3. Prior/Concomitant Medications/Procedures

Partially missing start/stop dates for prior/concomitant medications and partially missing start dates for prior/concomitant procedures will be imputed in the ADaM dataset for prior/concomitant medications/procedures. For prior/concomitant medications, if the stop date is complete with no missing year, month, or day, and the partially missing start date imputed by the rule below is after the stop date, then the start date will be imputed by the stop date.

Partially missing prior/concomitant medication/procedure start dates will be imputed by the earliest possible date given the non-missing field(s) of the date.

Partially missing prior/concomitant medication stop dates will be imputed by the latest possible date given the non-missing field(s) of the date.

16.3. International Myeloma Working Group Uniform Response Criteria**Table 6: International Myeloma Working Group Uniform Response Criteria**

Response Category	Response Criteria
Stringent Complete Response (sCR)	CR as defined below, plus Normal serum free light chain (FLC) ratio and Absence of clonal plasma cells by immunohistochemistry or 2- to 4-color flow cytometry
Complete Response (CR)	Negative immunofixation of serum and urine and Disappearance of any soft tissue plasmacytomas and ≤ 5% plasma cells in bone marrow In patients in whom the only measurable disease is by serum FLC levels: CR in such patients indicates a normal FLC ratio of 0.26 to 1.65 in addition to CR criteria listed above.

Table 6: International Myeloma Working Group Uniform Response Criteria (Continued)

Response Category	Response Criteria
Very Good Partial Response (VGPR)	
Serum and urine M-protein detectable by immunofixation but not on electrophoresis or
 
90% or greater reduction in serum M-protein plus urine M-protein level < 100 mg per 24 hours.
 
In patients in whom the only measurable disease is by serum FLC levels: VGPR in such patients requires a > 90% decrease in the difference between involved and uninvolved FLC levels.

Partial Response (PR)	
≥ 50% reduction of serum M-Protein and reduction in 24-hour urinary M-protein by ≥ 90% or to < 200 mg per 24 hours
 
If the serum and urine M-protein are not measurable, a ≥ 50% decrease in the difference between involved and uninvolved FLC levels is required in place of the M-protein criteria.
 
If serum and urine M-protein are unmeasurable, and the serum free light chain assay is also unmeasurable, a ≥ 50% reduction in plasma cells is required in place of M-protein, provided baseline bone marrow plasma cell percentage was ≥ 30%.
 
In addition to the above, if present at baseline a ≥ 50% reduction in the size of soft tissue plasmacytomas is also required.

Stable Disease (SD)	Not meeting criteria for CR, VGPR, PR, or PD
Progressive disease (PD)	
Requires only one of the following:
 
Increase of 25% from lowest response value in any of the following:
 
 • Serum M-component (absolute increase must be ≥ 0.5 g/dL), and/or • Urine M-component (absolute increase must be ≥ 200 mg/24 h), and/or 
Only in patients without measurable serum and urine M-protein levels: the difference between involved and uninvolved FLC levels (absolute increase must be ≥ 10 mg/dL)
 
Only in patients without measurable serum and urine M-protein levels and without measurable disease by FLC levels, bone marrow plasma cell percentage (absolute percentage must be ≥ 10%)
 
Definite development of new bone lesions or soft tissue plasmacytomas or definite increase in the size of existing bone lesions or soft tissue plasmacytomas
 
Development of hypercalcemia (corrected serum calcium > 11.5 mg/dL) that can be attributed solely to the plasma cell proliferative disorder

Table 6: International Myeloma Working Group Uniform Response Criteria (Continued)

Response Category	Response Criteria
Additional Response Criteria	
Molecular Complete Response	CR plus negative allele-specific oligonucleotide polymerase chain reaction (ASO-PCR), sensitivity 10^{-5}
Immuno-phenotypic Complete Response	Stringent CR plus Absence of phenotypically aberrant plasma cells (clonal) in BM with a minimum of 1 million total BM cells analyzed by multi-parametric flow cytometry (with > 4 colors)
Minimal Response (MR) in patients with relapsed refractory myeloma adopted from the European Group for Blood and Marrow Transplantation (EBMT) criteria	$\geq 25\%$ but $\leq 49\%$ reduction of serum M-protein and reduction in 24-hour urine M-protein by 50%-89% In addition to the above criteria, if present at baseline, 25%-49% reduction in the size of soft tissue plasmacytomas is also required No increase in size or number of lytic bone lesions (development of compression fracture does not exclude response)

BM = bone marrow; FLC = free light chain.

a All response categories (CR, sCR, VGPR, PR, and PD) require 2 consecutive assessments made at any time before the institution of any new therapy; CR, sCR, VGPR, PR, and SD categories also require no known evidence of progressive or new bone lesions if radiographic studies were performed. VGPR and CR categories require serum and urine studies regardless of whether disease at baseline was measurable on serum, urine, both, or neither. Radiographic studies are not required to satisfy these response requirements. Bone marrow assessments need not be confirmed. For PD, serum M-component increases of more than or equal to 1 g/dL are sufficient to define relapse if the starting M-component is ≥ 5 g/dL.

Source: Adapted from [Rajkumar, 2011](#).

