10.4. Progression-free survival

Progression-free survival (PFS) is defined as the time from treatment initiation to the first date of documented PD or death from any cause during the study whichever occurs earlier.

Subjects who do not have a PFS event will be censored on the last adequate assessment date. Progression-free survival will be summarized for the FAS using Kaplan-Meier (KM) statistics.

Subjects who had PD prior to receiving other antimyeloma therapy will be considered to have the event on the date of PD. Subjects who died without documented PD and without receiving other antimyeloma therapy will be considered to have an event on the date of death. Subjects who did not have disease progression at the time of the data cut-off date will be censored on the date of their last adequate response assessment on or prior to the cut-off date. For subjects with PD documented between scheduled assessments, the event will be considered to have occurred

on the date of last scheduled adequate assessments with no progression. The censoring rules for PFS are provided in [Table 5](#). These rules are based on the United States Food and Drug Administration (US FDA) guidance for cancer trial endpoints ([FDA Guidance, 2007](#)).

Table 5: Censoring Rules for Progression-free Survival

Situation	Date of Progression or Censoring	Situation Outcome
Death within the first two scheduled assessments without disease progression	Date of death	Event
Progression	If the first PD is a scheduled assessment, then Date of first PD; If the first PD is an unscheduled assessment and no previous assessment, then Date of PD; If the first PD is an unscheduled assessment and has previous assessment, then Date of previous assessment (regardless of the response type)	Event
Death between scheduled assessments	Date of death	Event
No progression	Date of last adequate assessment with evidence of no progression	Censored
Death or progression after two or more missed scheduled assessments	Date of last adequate assessment with evidence of no progression	Censored
New antimyeloma / non-protocol cancer treatment started prior to progression or death due to any reason	Date of last adequate assessment with evidence of no progression before the start of new treatment	Censored

PD = progressive disease.

Source: United States Food and Drug Administration (US FDA) guidance for cancer trial endpoints for the approval of cancer drugs and biologics ([FDA Guidance, 2007](#)).

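### SAP 16.2 gives conflicting imputation rules for partial medication dates and, separately, lets a partial new-therapy date be imputed ahead of a documented progression

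*SAP*

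**What the plan says.** **Medication dates, first rule set.** The heading "16.2.1. Impute Missing Adverse Events / Prior or Concomitant Medications" claims both data types. For starts, a missing day in a month before first dose goes to month end: "then the last day of the month will be assigned to the missing day". In the first-dose month, "then the first dosing date will be assigned to the missing day". In a later month it goes to the first of the month. If day and month are both missing and the year is that of first dose, "then the day and month of the first dosing date will be assigned to the missing fields"; an earlier year goes to 31 December and a later year to 1 January.

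**Medication dates, second rule set.** SAP 16.2.3 covers the same medications: "Partially missing prior/concomitant medication/procedure start dates will be imputed by the earliest possible date given the non-missing field(s) of the date". Stop dates go to the latest possible date. Neither section says which prevails.

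**Stop dates within 16.2.1.** For a year-only stop, one bullet sends any year before the last-dose year to 31 December. The next takes a stop year that also precedes the last-dose year "but is the same as the year of the first dosing date, then the first dosing date will be assigned to the missing date".

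**AE end dates.** SAP 16.1 counts them among the log dates to be imputed under 16.2, and 16.2.1 has stop-date bullets. SAP 16.2.2 says "partially missing AE end dates will not be imputed in the same dataset".

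**Where a therapy date matters.** Table 5 in SAP 10.4 censors PFS for "New antimyeloma / non-protocol cancer treatment started prior to progression or death due to any reason", at the latest adequate progression-free assessment ahead of that treatment. DOR uses the same rules (10.3) and TTP similar ones (10.5). Under 16.1, progression dates are not imputed.

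**The concern.** Two programmers could each follow the SAP and produce different medication datasets, with different prior and concomitant flags.

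The second issue concerns order. Table 5 turns on whether new therapy comes before or after progression. The progression date is fixed, so only a partial therapy date can move, and the start-date rules move it backwards whenever the recorded month or year follows first dose. Subjects stay on treatment until progression or unacceptable toxicity (Protocol 3.2), so therapy after progression is the natural sequence, and backdating can reverse it. A subject who progressed would then be censored just before progressing. That generally pushes Kaplan-Meier PFS and DOR upward, in a single-arm trial with no comparator to absorb the bias.

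**Working it through.** No sample size or error rate is involved, so there is no plan figure to reproduce. The check applies the rules literally to illustrative dates.

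**Step 1. Do the rule sets agree?** Assume first dose 15 Mar 2017 and last dose 12 Sep 2017.

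| Recorded | 16.2.1 | 16.2.3 |
|---|---|---|
| Start Feb 2017 | 28 Feb 2017 | 1 Feb 2017 |
| Start Mar 2017 | 15 Mar 2017 | 1 Mar 2017 |
| Start 2016 | 31 Dec 2016 | 1 Jan 2016 |
| Start 2017 | 15 Mar 2017 | 1 Jan 2017 |
| Start Oct 2017 | 1 Oct 2017 | 1 Oct 2017 |
| Start 2018 | 1 Jan 2018 | 1 Jan 2018 |
| Stop Sep 2017 | 12 Sep 2017 | 30 Sep 2017 |
| Stop 2017 | 12 Sep 2017 | 31 Dec 2017 |
| Stop 2018 | 1 Jan 2018 | 31 Dec 2018 |

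A start recorded as Mar 2017 or 2017 changes class: on the first-dose date it is concomitant only, whereas before that date it is a prior medication (SAP 8.7.1, 8.7.2). The Feb 2017 and 2016 rows change the date but not the class.

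**Step 2. Does 16.2.1 agree with itself?** Move last dose to 1 Feb 2018 and record a stop as 2017. One bullet gives 31 Dec 2017 and the next gives 15 Mar 2017.

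**Step 3. Can a true progression be censored?** With first dose on 15 Mar 2017 and 28-day cycles, Day 1 visits fall on 12 Apr, 10 May, 7 Jun and 5 Jul. Suppose progression is documented on 7 Jun and confirmed at an unscheduled visit, and new therapy starts on 21 Jun but is recorded as Jun 2017. Both rules give 1 Jun, before progression. Table 5 then replaces an event 84 days after first dose (3 × 28) with a censored time at 10 May, 56 days after first dose (2 × 28).

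If confirmation waits for 5 Jul and therapy is recorded as Jul 2017, both rules give 1 Jul, after 7 Jun, and the event stands.

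**Step 4. How often, among partial dates?** Take each day from 1 Jun 2017 to 31 May 2018 (365 days) as the progression date, with therapy g days later. The gaps are assumptions; the documents give none.

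Day missing: the order reverses when therapy falls in the same month as progression and progression is not on the first. A month of L days contributes max(0, L − g − 1) dates.

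- g = 1: 365 − 12 × 2 = 341; 341/365 = 93%
- g = 7: 365 − 12 × 8 = 269; 74%
- g = 14: 365 − 12 × 15 = 185; 51%
- g = 21: 365 − 12 × 22 = 101; 28%
- g = 28: seven 31-day months × 2 plus four 30-day months × 1 = 18; 5%
- g = 35: 0%

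Day and month missing: of 214 progression dates in 2017, 214 − g reverse; of 151 in 2018, all but 1 January do. The total is 364 − g, so 363/365 = 99.5% at g = 1 and 329/365 = 90% at g = 35.

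Both rule sets give identical percentages. These are shares of subjects whose new-therapy date is partial, not shares of all subjects.

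**The case against.** **Source of the date.** The SAP does not say that Table 5 reads the medication log. The documents elsewhere keep myeloma therapy apart: Protocol Table 4 has its own row for earlier disease therapies, Protocol 6.1 leaves drugs taken for the disease out of the screening medication review, and SAP 8.5 is separate from 8.7. This stands as a limit. Those places concern therapy before the study, however. SAP 8.7.2 counts any drug started on study through 90 days after last dose as concomitant, with no exclusion for antimyeloma drugs, and Protocol Section 8 requires concomitant treatments in that window on the eCRF. If a separate form exists, the SAP shows no rule for its partial dates; nor does 8.7.2 reach therapy begun after 90 days.

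**Confirmation.** Progression needs two consecutive assessments before new therapy, except radiographic or marrow findings (Protocol 6.4.5.2, Appendix B). With visits every 28 days, many next regimens start in a later month. This stands and makes reversal less common. Backdating of progression found at an unscheduled visit (Table 5) would reduce it further if the comparison uses the backdated date, which the SAP does not specify.

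**Importance.** SAP 16.1 expects log dates to be complete, and PFS, DOR and TTP are secondary and descriptive. The AE end-date conflict matters little: 16.2.2 is the specific rule for that dataset, and treatment-emergent status depends on onset or worsening. All of this stands.

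**Outcome-dependent repair.** Placing therapy after progression uses the outcome to set the date. That is a fair criticism, but confirmed progression already requires assessments made before new therapy, so the assumed order matches the response criteria.

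**Conclusion.** Both faults hold, and they are independent.

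The rule conflict is on the page and needs no assumption. Its shown effect is on prior/concomitant flags and medication summaries.

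The false censoring is conditional on the Table 5 new-therapy date coming from the medication log. Given that, a day-missing start in a month after first dose goes to the first of that month under either rule, and same-month therapy after progression is placed before it. A year-only start goes to the first dosing date (16.2.1) or 1 January (16.2.3) in the first-dose year, and to 1 January in a later year. PFS, DOR and TTP can be affected.

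Four stronger readings are tempting and not supported:

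- That the conflict causes the false censoring, so choosing one rule cures it. Both rules give the same date in the usual case, so it does not.
- That a year-only date always censors PFS at about Day 1. That applies only in the first-dose year.
- That a count of lost events, or a shift in median PFS or DOR, can be stated. The documents give neither the rate of partial dates nor an expected number of events.
- That the response decisions at 3 of 18 and 9 of 50 are at risk. ORR does not use Table 5 censoring.

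**What to change.** **Rule conflict.** Keep the 16.2.1 start-date bullets for AEs only. Delete its stop-date bullets and its medication scope. Let 16.2.2 govern AE end dates and 16.2.3 govern medications. Align the 16.1 sentence on log dates, and point 16.2.2 to 16.2.1 for AE starts; it now refers to rules below it, where only the medication rules stand.

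**New-therapy date.** Name the data source in Table 5. Add a rule that a partial start of new antimyeloma therapy is imputed as the latest of the first day of the recorded period, the day after last study dose and the day after documented progression, capped at the last day of the recorded period. Omit the progression term when progression falls after that period, since the record then already places therapy first. List every imputed case.

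In the Step 4 enumeration, not imputing before a progression date that the recorded period allows takes false censoring to 0% at every gap. The small downside is that therapy truly begun before progression within the recorded period would be counted as an event; the listing lets a reader see how many subjects this could concern.

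**Cost.** Appendix wording and one derivation, before database lock. No new data.
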